***PREDICTION AND MAINTENANCE OF SINUS RHYTHM
AMONG ATRIAL FIBRILLATION PATIENTS***

Principal Investigator: *[name]*

[NCT Number: NCT04313296](#)

List of Abbreviations

AF: Atrial Fibrillation

EPIC: the electronic medical record system utilized by Pen Bay Medical Center

COPD: Chronic Obstructive Pulmonary Disease

LA GLS - left atrial global longitudinal strain

LAVI (Left atrial volume index)

PBMC: Pen Bay Medical Center

PHI: Protected Health Information

REDCap: Research Electronic Data Capture

TOMTECH – ARENA: echocardiographic software program

1 Introduction

Atrial fibrillation (AF) is the most common heart rhythm disorder seen in clinical practice, with an estimated 2.7-6.1 million people in the U.S. affected by the disorder [1]. Previous studies have demonstrated that left atrial volume is a predictive measure of incident atrial fibrillation [2]. This study aims to add to the literature by investigating predictive measures of left atrial global longitudinal strain (LA GLS) that would be suggestive of maintenance of normal sinus rhythm post cardioversion. If we could gain insight on the connection between LA GLS and cardioversion among patients with atrial fibrillation, we could potentially help the clinical management of patients pre/post cardioversion, and potentially change poor outcomes.

Background

Atrial fibrillation (AF) is a heart rhythm disorder in which the normal beating in the upper chambers of the heart is irregular, leading to poor blood flow to the lower chambers. Risk factors include older age, high blood pressure, obesity, European ancestry, diabetes, heart failure, ischemic heart disease, hyperthyroidism, chronic kidney disease, heavy alcohol use, and enlarged heart chambers on the left side [3]. AF increases a person's risk for stroke and contributes to an estimated 130,000 deaths each year [1]. Treatment generally includes medication, surgery, and/or healthy lifestyle changes [1]. Electrical cardioversion, in which the patient must undergo sedation or general anesthesia, is also used to convert patients with persistent AF to normal sinus rhythm. Electrical cardioversion has been associated with a high initial success rate of 68-98% [4], but long-term maintenance of sinus rhythm has proved challenging [5]. Due to the potential risks incurred to the patient, it is important to understand which patients are good candidates for cardioversion therapy. A review article describes that duration of AF, sex, age, weight, smoking status, number of shocks at cardioversion, post-ablation procedure, medications, hypertension, diabetes, Chronic Obstructive Pulmonary Disease (COPD), obstructive sleep apnea, renal impairment, hyperthyroidism, coronary artery disease, congestive heart failure, left systolic dysfunction, left diastolic dysfunction, left ventricular hypertrophy, valvular heart disease, and left atrial size have each been found to be associated with maintenance of sinus rhythm [6].

Echocardiography has been increasing used in understanding the cardiac structure and risk of stroke among patients with AF, with left atrial size, left ventricular wall thickness, and left ventricular dysfunction recognized as independent predictors of AF [7]. Increasing evidence supports that the left atrial strain measurements can be a predictor of outcomes among AF patients, including stroke and AF recurrence after catheter ablation [8], [9]. We aim to further explore left atrial strain measurements, including left atrial global longitudinal strain (LA GLS), as predictors of maintenance of normal sinus rhythm post-cardioversion. We anticipate to find that a lower LA GLS will predict AF recurrence. To do this, we will study patients with AF at Pen Bay Medical Center who have undergone cardioversion, measuring their LA GLS pre-cardioversion, and assess maintenance of sinus rhythm 6 months post-cardioversion. We anticipate that our study will confirm LA GLS as a marker for maintenance of sinus rhythm post-cardioversion.

Hypothesis

A lower left atrial global longitudinal strain is a predictor of atrial fibrillation recurrence post- electrical cardioversion.

Specific Aims

Include patients from the MaineHealth system into a retrospective study to explore the relationship between left atrial global longitudinal strain (LA GLS) and AF. Patient data will derive from existing EPIC data for MaineHealth patients from January 1, 2017 to June 30, 2021. The EPIC data extract will include: diagnosis of atrial fibrillation, documented echocardiogram, and electrical cardioversion during the study time period. For patients who meet the study criteria outlined in Section 3 below, we will collect demographic and clinical data from EPIC manually (see Section 5 below). The primary outcome measure to be collected includes maintenance of sinus rhythm at least six months post-cardioversion.

Include patients from Pen Bay Medical Center (PBMC) into the same study, however in a prospective portion of the study. These patients will be consented and followed prospectively until six months after cardioversion.

2. We will assess LA GLS using an automated measurement tool called AutoSTRAIN by TOMTEC-ARENA (<https://www.tomtec.de/products/application-finder/autostain/>). The historic echocardiograms from patients who meet the study inclusion criteria will be uploaded into this software, which was newly acquired by the PBMC Cardiology Department. MaineHealth Information Services are currently working with study staff to assure appropriate security compliance within the network. LA GLS has not been routinely collected previously from echocardiograms performed at PBMC because of a lack of such technology.
3. We will use statistical methods to describe the relationship between LA GLS and maintenance of sinus rhythm six months post-cardioversion among the AF patients included in this study.

2 Study Design

This study has both retrospective and prospective components. There is an enrollment goal of 500 subjects.

For the retrospective portion, patients will be identified for inclusion in the study based on a previous documented diagnosis of AF, have a documented echocardiogram done prior to the cardioversion with images available in the MaineHealth electronic medical record (EMR), and have undergone electrical cardioversion at a MaineHealth institution.

For the prospective portion of the study, patients will be identified by the PBMC echocardiographic technicians prior to elective cardioversion. The patient will be consented prior to the administration of any sedative. If the patient consents, they will be followed for 6 months after the procedure via the EMR only. The prospective portion of the study will only be conducted at PBMC and not at other MaineHealth institutions due to the lack of staffing capacity at the investigative site.

3 Subject Selection and Withdrawal (if applicable)

3.1 *Inclusion Criteria*

- Patients identified at any MaineHealth site with a documented diagnosis of AF (at any point in time prior to the cardioversion) and who have undergone any cardioversion.
- The patient would also need to have had an echocardiogram within six months pre-cardioversion (performed for any reason) with a well visualized atrial roof in order to perform the measurements accurately using the TOMTEC-ARENA software.
- For the prospective portion of the study – must be willing to provide informed consent

3.2 *Exclusion Criteria*

- Patients with a mitral regurgitation greater than moderate (effective regurgitant orifice $\geq .2 \text{ mm}^2$)
- Patients who have undergone surgical valve repair or replacement, if the procedure was done with a thoracotomy
- Echocardiographic images not of sufficient quality to obtain the study measurements as determined by the investigator

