3.3 Subject Recruitment and Screening

Subjects will be identified using a retrospective chart review within EPIC, between January 1, 2017, through June 30, 2021. These patients will have a diagnosis of atrial fibrillation, a documented echocardiogram, and cardioversion therapy. The study staff will review the medical records in EPIC of these patients and screen for the other inclusion/exclusion elements described above.

For the prospective portion of the study, potential subjects will be identified by the PBMC echocardiographic technicians prior to cardioversion. Either one of the echocardiographic technicians or one of the PBMC Clinical Research coordinators will explain the study to the patient and obtain informed consent.

4 Storage of Study Materials

Study data will be entered into and maintained in a web-based, HIPAA-compliant REDCap database which has a password protected login and only accessed by appointed study staff. These staff include a cardiac sonographer, the clinical research manager at PBMC, and the Rural Research Navigator at the Center for Outcomes Research and Evaluation (CORE), each of which will have full read/write access to the database. Information about study subjects will be kept confidential and managed according to the requirements of the Health Insurance Portability and Accountability Act of 1996 (HIPAA). Once the dataset is complete, all identifiers (medical record numbers and dates of health events or services) will be deleted and subjects will be identified by a unique study ID#, assigned by REDCap. Only de-identified data will be downloaded for analysis.

5 Data collection and management

The study staff- one cardiac sonographer, the clinical research manager at PBMC, and the Rural Research Navigator at CORE- will request an extract of EPIC patient data from Enterprise Reporting based on the inclusion criteria of atrial fibrillation, a documented echocardiogram, and electrical cardioversion therapy, including these codes:

	ICD-9	ICD-10	CPT
Atrial fibrillation	427.31		
Atrial flutter	427.32		
Paroxysmal atrial fibrillation		I48.0	
Persistent atrial fibrillation		I48.1	
Chronic atrial fibrillation		I48.2	
Typical atrial flutter		I48.3	
Atypical atrial flutter		I48.4	
Unspecified atrial fibrillation		I48.91	
Unspecified atrial flutter		I48.92	
Transthoracic stress echo, complete			93350
Transthoracic stress echo, complete w cont EKG			93351
Transthoracic echo cardiac anomalies			93303

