Transthoracic echo cardiac anomalies, limited			93304
Transthoracic echo complete w color & spectral			93306
Transthoracic echo complete wo color & spectral			93307
Transthoracic echo limited			93308
Cardioversion (nonemergency), elective, electrical			92960

The study staff will review the medical records in EPIC of these patients and screen for the other inclusion/exclusion elements described above. Patients who meet this criteria will be included in the study and have their medical record number documented in REDCap (a secure, HIPAA compliant, web-based database portal). If these patients are living and scheduled for a follow-up visit at PBMC, they will be consented to be included in the study by one of the study staff. If they do not consent to be included in the study, their information will be deleted from the REDCap database. If they are no longer living or have already had a follow-up visit at the time of the study start date, consent will not be obtained. For those included in the study, medical record numbers, along with demographics, BMI, date of atrial fibrillation diagnosis, antiarrhythmic medications, date(s) of echocardiogram(s) and cardioversion(s) performed, and whether sinus rhythm was maintained at least six months post-cardioversion either by electrocardiogram (ECG), holter monitor, telemetry monitoring or cardiologist dictated note. These patients' echocardiography images will be obtained pre-cardioversion from EPIC and uploaded to the TOMTEC software in order to obtain the LA GLS measurements (as continuous data).

GLS is derived via validated methods [10] using a calculation of:
$$\epsilon = \frac{L1 - L0}{L0} \times 100\%$$

It has proven to be clinically reproducible as reported in a prior study [11]. While the TOMTEC vendor does not provide normal range values for clinical interpretation, the literature provides GLS measurement data for comparison among nine different software vendors, including TOMTEC [12].

In short, we will:

1. Identify patients at with AF, who obtained an echocardiogram and cardioversion.
2. Consent patients who meet the inclusion criteria who are living and who will be returning for their six month follow-up visit.
3. For patients who have consented or who are deceased, or who have already presented for their six month follow-up visit by the time the study has started, the following information will be collected:
 - a. Dates of echocardiogram(s) and cardioversion(s) performed

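### One calendar window covers the retrospective EPIC data, with no echo look-back and no outcome cut-off, so early-2017 patients can be missed and the last six months of cardioversions may not be evaluable

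*Combined protocol and SAP*

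**What the plan says.** Specific Aims gives one window for the retrospective portion: "Patient data will derive from existing EPIC data for MaineHealth patients from January 1, 2017 to June 30, 2021". The extract is to contain "diagnosis of atrial fibrillation, documented echocardiogram, and electrical cardioversion during the study time period". Section 3.3 repeats the dates: "Subjects will be identified using a retrospective chart review within EPIC, between January 1, 2017, through June 30, 2021".

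The eligibility criteria in Section 3.1 reach further back. On imaging, "The patient would also need to have had an echocardiogram within six months pre-cardioversion". On diagnosis, the criterion is a "documented diagnosis of AF (at any point in time prior to the cardioversion" itself. Neither has a calendar floor.

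The outcome reaches forward: "The primary outcome measure to be collected includes maintenance of sinus rhythm at least six months post-cardioversion".

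Section 5 deals with patients whose follow-up visit is still to come: "If these patients are living and scheduled for a follow-up visit at PBMC, they will be consented to be included in the study". The numbered summary later in Section 5 repeats the consent step without naming a site. Section 5 also keeps record numbers and event dates until the six-month visit has been documented, and then removes them.

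Nowhere does the document give an earlier start for echocardiograms, an earlier last date for cardioversions, or a closing date for rhythm records.

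**The concern.** A design that looks back six months from cardioversion and forward six months needs an observation period longer than its index period at both ends. Here one pair of dates serves for everything that is dated.

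At the front, the extract is narrower than the eligibility criteria. Screening starts from the extract, so staff would never see an eligible patient whose echocardiogram predates January 2017. Section 8 already expresses doubt about reaching 500.

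At the tail, a patient cardioverted after December 2020 could be seen to relapse by 30 June 2021 but could not, on the stated window, be documented as maintained at six months. Two abstractors could treat the same patient differently: one would stop at the window and the other would read on.

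This is hard to repair later. Sections 4 and 5 delete the dates and release only de-identified data for analysis. The calculated fields named are the echocardiogram time lapse and AF duration; no interval from cardioversion to rhythm record is named. After deletion the analyst could not tell which patients came from the last six months.

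**Working it through.** The 500 in Section 2 comes with no derivation, so there is no planned figure to reproduce. The check is date arithmetic.

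**Inputs from the document**
- Window: 1 January 2017 to 30 June 2021 (Specific Aims, Section 3.3).
- Echo look-back: up to 6 months (Section 3.1).
- Follow-up: at least 6 months (Specific Aims).
- Target: 500, both portions combined, split not given (Section 2).

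**Assumptions**
- Cardioversions accrue evenly over the window.
- At the front, a patient has no second qualifying echocardiogram inside the window.

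**Length of the window**
- 365 + 365 + 365 + 366 + 181 = 1,642 days, or 54 months.

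**Front**
- A cardioversion t months into the window loses its echocardiogram if the lag L exceeds t. With t even over 54 months, the expected share lost is (mean of L)/54.
- Mean lag 1 month: 1/54 = 1.9%.
- Mean lag 3 months (for example, lags uniform over 0 to 6): 3/54 = 5.6%.
- Ceiling, every lag 6 months: 6/54 = 11.1%.
- The document gives no lag distribution. If echocardiograms cluster close to cardioversion, the loss is at the low end.

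**AF diagnosis**
- Read as an in-window requirement, the extract rule also conflicts with Section 3.1. The effect on yield is probably small, because AF is likely to be coded again around the cardioversion.

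**Tail, reading the window literally**
- The last cardioversion that can reach six months by 30 June 2021 falls at the end of December 2020.
- 1 January to 30 June 2021 = 181 days; 181/1,642 = 11.0%.
- In patients: 500 × 0.110 = 55 if all 500 were retrospective, 400 × 0.110 = 44, and 300 × 0.110 = 33.

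**With separate dates**
- 1 January 2017 less six months is 1 July 2016; 30 June 2021 plus six months is 30 December 2021. Echocardiograms from the first date and rhythm records through 31 December 2021 bring both losses to zero, where the images and records exist.

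**The case against.** The strongest reply concerns the tail. A reader might infer that outcome collection itself closes on 30 June 2021, so that later cardioversions can never yield a six-month result. The document does not go that far. The outcome is not among the items tied to the study period, Section 3.3 uses the dates to identify subjects, and Section 5 provides for visits still to come and holds record numbers so that later rhythm information can be linked. Nor is the chart review dated; if it runs after December 2021, the records will exist. This stands, and the tail problem holds only on the literal window. It does not close the gap: the consent text names PBMC while the retrospective cohort is system-wide, and collecting later visits sits awkwardly with a source described as existing data for fixed dates.

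A second reply is grammatical: the study-period phrase may govern only the cardioversion, in which case the front loss and the diagnosis conflict both disappear. That reading is possible but not the natural one for a three-item list, and the data request must settle it either way.

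A reader might also infer that the observed recurrence rate is inflated, or that the LA GLS comparison is biased, because relapse is visible in the tail and maintenance is not. No passage says that patients without a six-month record count as recurrences; if they are not evaluable, the effect is lost sample. Section 6 compares mean LA GLS by outcome and fits a logistic model, and selection on outcome alone mainly moves the intercept of such a model. No bias in the LA GLS result is shown.

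**Conclusion.** The concern stands as a conflict between the extract dates and the eligibility criteria at the front, and as an unstated outcome cut-off at the tail.

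The front loss is between about 2% and 6% of retrospective cardioversions for mean lags of one to three months, with a ceiling of about 11%. It rests on even accrual, on no second qualifying echocardiogram in the window, and on the natural reading of the extract rule.

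The tail exposure is 11.0% of the window, which is date arithmetic. Turning it into patients needs even accrual and the retrospective share of the 500, which is not stated; about 55 applies only if all 500 are retrospective. Whether those patients are actually lost depends on how the window is read and is least clear for MaineHealth sites other than PBMC.

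The consequence supported by the document is avoidable loss of eligible or evaluable patients and inconsistent abstraction. This is more than missing detail, because the dates needed to sort it out are to be deleted.

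**What to change.** In Specific Aims and Section 3.3, replace the single window with separate dates for each element:

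- Index cardioversion: 1 January 2017 to 30 June 2021.
- Qualifying echocardiogram: from 1 July 2016, where images are available in the EMR. The document does not say whether 2016 images are held, so this must be confirmed.
- AF diagnosis: any time before cardioversion, as Section 3.1 already has it.
- Rhythm records: through at least 31 December 2021, for all sites.

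In Section 5, say whether the consent step for visits still to come applies at sites other than PBMC. In Section 6, say how patients without a six-month rhythm record are handled. Make these changes before the extract is run and before dates are removed from REDCap.

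The cost is a wording change and wider dates in one data request, with no new procedures. If rhythm records after June 2021 cannot be obtained, end index cardioversions at 31 December 2020; that gives up about 11% of the retrospective cohort under even accrual.

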- Protected health information (PHI), which will be collected from subject charts in this study, include demographics (age, sex), echocardiogram results, and maintenance of normal sinus rhythm. Patient medical record numbers will be used for linking the prospective information related to maintenance of normal sinus rhythm, and will be deleted after this information is documented in REDCap.
- Time lapsed between echocardiogram(s) and duration of atrial fibrillation will be calculated fields created in REDCap based on dates of echocardiogram(s) and date of first atrial fibrillation diagnosis, respectively. Once the time lapsed variables have been created, the date variables will be removed from the database.
- Only the cardiac sonographers and the PBMC clinical research nurse manager will have access to this information.

6 Analysis Plan

The duration of AF will be calculated for each patient utilizing the date of first AF diagnosis and the date(s) of cardioversion(s). Descriptive statistics will be used to summarize the demographic and clinical characteristics of patients included in the study, with continuous variables presented as a mean + standard deviation and categorical variables as frequencies/percentages of the total.

A t-test will be utilized to compare the mean LA GLS among patients documented to have maintenance of sinus rhythm at 6 months to those who have not.

A binary logistic regression model will be developed in order to model any predictive factors (independent variable: echocardiographic features/measurements) among those who have maintained sinus rhythm vs. those who have not (dependent variable: sinus rhythm yes/no) within six months of cardioversion. Criteria for selecting other variables listed above for entry into the logistic regression model will be based on univariate analysis of each variable. Variables determined to have a significant univariate test with a p-value cutoff of 0.05 will be included in the model. Variables deemed not significant will be assessed for confounding by observing parameter estimate changes >10% when variables are excluded from the full model. Analyses will be performed using SAS by the Rural Research Navigator at the Center for Outcomes Research and Evaluation at the Maine Medical Center Research Institute.

7 Confidentiality

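### Multi-site retrospective and PBMC-only prospective patients appear to be analysed together with no site or component variable, so the LA GLS comparison cannot be checked or adjusted for either

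*Combined protocol and SAP*

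**What the plan says.** Section 2: "This study has both retrospective and prospective components", and "There is an enrollment goal of 500 subjects". The goal is not divided between components.

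The sources differ. Section 3.1 admits "Patients identified at any MaineHealth site with a documented diagnosis of AF", and Section 3.3 sets the chart review at January 2017 to June 2021. For the other component, Section 2 says "The prospective portion of the study will only be conducted at PBMC and not at other MaineHealth institutions". The Specific Aims join the two: "Include patients from Pen Bay Medical Center (PBMC) into the same study, however in a prospective portion of the study".

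Consent differs too. Prospective patients must consent. Under Section 5, chart-review patients who are living and still due for a PBMC follow-up visit must also consent and are deleted if they refuse. Those who have died or have already been seen enter without consent.

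The itemised list in Section 5 covers sex, age, comorbidities, antiarrhythmic drugs, number of shocks, LA GLS in two views, LAVI and other patient factors. It has no field for site or component.

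Section 6 plans one unadjusted t-test of LA GLS by rhythm outcome and one logistic model. On covariates it says: "Criteria for selecting other variables listed above for entry into the logistic regression model will be based on univariate analysis". No stratification, site or component term, or analysis by component is planned. Section 4 deletes record numbers and dates once the dataset is complete, and only de-identified data go to analysis.

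**The concern.** Two groups assembled in different ways enter one comparison. Suppose mean LA GLS differs between sites or components, through case mix or image acquisition. Suppose also that the share recorded as maintaining sinus rhythm differs, through local practice or patient selection. Then patients with and without recurrence contain different mixes of the groups, and LA GLS differs between them even if it predicts nothing within any group. The distortion can imitate the hypothesised effect or hide a real one.

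The planned confounding check, which looks for a change of more than 10% in the estimate, cannot detect this because it can only act on variables that were collected. Once record numbers and dates are gone, they cannot be used to reconstruct component, site or period.

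**Working it through.** **The plan's figure.** The documents give no power, effect size, SD, recurrence rate or component split, so 500 cannot be reproduced. It is used here only as the total N.

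**Inputs.** From the documents: N = 500 (Section 2). Assumed: a two-sided 5% test (Section 6 gives 0.05 only as the covariate entry cut-off); no LA GLS effect within either stratum; a gap g of 0.2, 0.4 or 0.6 SD in mean LA GLS; recurrence of 40% in the smaller stratum B against 50%, 55% or 60% in A; share f of stratum B equal to 50%, 20% or 10%.

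**Formulas.**
- Pooled share maintained: p = 1 − [(1−f)·r_A + f·r_B]
- Share of B among maintained: a = f(1−r_B)/p
- Share of B among recurrences: b = f·r_B/(1−p)
- Spurious difference in SD: d = g(a − b)
- SE = √[1/(Np) + 1/(N(1−p))], and m = d/SE
- False-positive rate = 1 − Φ(1.96 − m) + Φ(−1.96 − m)

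**Equal strata, largest gaps.** p = 0.50, a = 0.5×0.6/0.5 = 0.6, b = 0.5×0.4/0.5 = 0.4. d = 0.6×0.2 = 0.12 SD. SE = √(2/250) = 0.0894. m = 1.34, giving 26.9%.

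**Same gaps, f = 0.2.** p = 1 − (0.8×0.6 + 0.2×0.4) = 0.44, a = 0.12/0.44 = 0.273, b = 0.08/0.56 = 0.143. d = 0.6×0.130 = 0.078 SD. SE = √(1/220 + 1/280) = 0.0901. m = 0.865, giving 13.9%.

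| LA GLS gap; recurrence B v A | f = 50% | f = 20% | f = 10% |
|---|---|---|---|
| 0.2 SD; 40% v 50% | d 0.020; 5.6% | d 0.013; 5.2% | d 0.007; 5.1% |
| 0.4 SD; 40% v 55% | d 0.060; 10.3% | d 0.038; 7.1% | d 0.022; 5.7% |
| 0.6 SD; 40% v 60% | d 0.120; 26.9% | d 0.078; 13.9% | d 0.044; 7.8% |

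The SE above ignores the variance that the gap itself adds to LA GLS. Counting it lowers the last row to 25.1%, 13.4% and 7.7%. Giving the smaller stratum the higher recurrence instead moves no rate by more than 0.1 point. If g = 0 or r_A = r_B, then d = 0 and the rate is 5%.

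**Does a component term work?** Twelve scenarios were simulated with 2,000 runs each: prospective share 20%, 30% or 50%, sinus-rhythm rate 50% in the retrospective group and 10 or 20 points lower in the prospective group, and a gap of 0.25 or 0.5 SD. The pooled t-test rejected in 5.2 to 21.1% of runs. A linear model of LA GLS on outcome and component rejected in 4.1 to 5.9%. This bears on the adjusted difference; the logistic model was not simulated.

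**The case against.** Much can be said in the plan's defence, and most of it limits the size of the problem without removing it.

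- **Follow-up.** A reader might infer that horizons differ by design, because the Specific Aims set "maintenance of sinus rhythm at least six months post-cardioversion" for the chart review, while for prospective patients "they will be followed for 6 months after the procedure via the EMR only". The documents do not establish this. Section 5 applies the six-month minimum to every included patient, Section 6 uses one outcome for all, and both components rely on routine records.
- **Elective against other cases.** Section 3.1 is broad, but the only cardioversion code in the retrospective extract is 92960, which is elective.
- **Echo laboratory.** One automated tool and two sonographers produce every LA GLS value, and poor images are excluded. Reading and vendor differences are largely removed; differences in acquisition and case mix are not.
- **Odds ratio.** The logistic model can adjust for LAVI and more than 20 patient factors. A reader might infer that the odds ratio is confounded by site. That is possible but not shown: the figures above concern the unadjusted t-test only.
- **Irreversibility.** A reader might infer that site and component can never enter the model or be recovered. That goes too far. The itemised list is not strictly closed, since BMI appears in the text of Section 5 but not in the list. Section 4 deletes record numbers and dates and keeps a study ID; it does not say that a recorded site or component field would be removed.
- **Split.** Equal strata give close to the largest bias. The prospective component is one hospital, so its share may be small, although a PBMC/other split could be more even.

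What remains is that the plan as written neither collects the two variables nor provides for adjusting on them.

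**Conclusion.** The concern holds as a conditional risk. Pooling is inferred from the single goal and the single analysis. Bias requires site or component to be related to both LA GLS and recorded sinus rhythm, and the documents give no figure for either gap or for the split. The false-positive rates therefore show a range under assumptions; none of them is a forecast, and 26.9% in particular belongs to the most unfavourable combination tried. With a 10% stratum the inflation is at most about 3 points, and with no gap there is none.

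The case for acting is that the omission is easily corrected before de-identification and harder to correct afterwards. The varying wording of the six-month outcome (a minimum of six months, at six months, within six months) is a separate matter that a site or component term does not resolve.

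**What to change.** 1. Add two fields to the Section 5 list: study component (retrospective/prospective) and site (PBMC/other). State in Section 4 that both stay in the de-identified dataset.
2. In Section 6, include both in the logistic model regardless of their univariate p-values.
3. Report the LA GLS difference adjusted for both, for example from a linear model of LA GLS on outcome, component and site, beside the planned t-test.
4. State in Section 6 that the components are pooled, if that is the intention.

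Because all prospective patients are at PBMC, the two terms can be separated only if the retrospective group contains PBMC patients as well as others. Section 3.1 allows this, and the counts should be tabulated first.

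The cost is two fields already known to study staff and two degrees of freedom. The number of sites is not stated, so finer site coding should depend on the number of patients per site.
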